6.4 Hepatotoxicity Stopping and Rechallenge Rules

Subjects with abnormal hepatic laboratory values (ie, ALP, aspartate aminotransferase [AST], alanine aminotransferase [ALT], total bilirubin [TBL]) and/or international normalized ratio (INR) and/or signs/symptoms of hepatitis (as described below) may meet the criteria for withholding or permanent discontinuation of Amgen investigational product or other protocol-required therapies as specified in the Guidance for Industry Drug-Induced Liver Injury: Premarketing Clinical Evaluation, July 2009.

6.4.1 Criteria for Permanent Withholding of AMG 416 due to Potential Hepatotoxicity

AMG 416 should be discontinued permanently and the subject should be followed according to the recommendations in [Appendix A](#) (Additional Safety Assessment Information) for possible drug-induced liver injury (DILI), if ALL of the criteria below are met:

- Increased AST or ALT from the relevant baseline value as specified below:

Baseline AST or ALT value	AST or ALT elevation
< ULN	> 3x ULN

AND

- TBL > 2 X the upper limit of normal (ULN) or INR > 1.5

AND

- No other cause for the combination of the above laboratory abnormalities is immediately apparent; important alternative causes for elevated AST/ALT and/or TBL values include, but are not limited to:
 - Hepatobiliary tract disease (obstructive gall bladder or bile duct disease)

- Viral hepatitis (eg, Hepatitis A/B/C/D/E, Epstein-Barr virus, cytomegalovirus, herpes simplex virus, varicella, toxoplasmosis, and parvovirus)
- Right-sided heart failure, hypotension, or any cause of hypoxia to the liver causing ischemia
- Exposure to hepatotoxic agents/drugs or hepatotoxins, including herbal and dietary supplements, plants, and mushrooms
- Heritable disorders causing impaired glucuronidation (eg, Gilbert's syndrome, Crigler-Najjar syndrome) and drugs that inhibit bilirubin glucuronidation (eg, indinavir, atazanavir)
- Alpha-one antitrypsin deficiency
- Alcoholic hepatitis
- Autoimmune hepatitis
- Wilson's disease and hemochromatosis
- Non-alcoholic fatty liver disease including steatohepatitis
- Non-hepatic causes (eg, rhabdomyolysis, hemolysis)

If an alternative cause for hepatotoxicity is identified or less stringent conditions developed than what are noted above, determine (based on subject population and/or severity of the hepatotoxicity or event) if AMG 416 and other protocol-required therapies should be withheld or permanently discontinued, as deemed appropriate for the safety of the subject.

6.5 Concomitant Therapy

Throughout the study, investigators may prescribe any concomitant medications or treatments deemed necessary to provide adequate supportive care except for those listed in [Section 6.9](#). Concomitant therapies are to be collected from informed consent through the EOS. Collect therapy name, indication, dose, unit, frequency and route, start date, and stop date.

Details of all concomitant medications will be recorded in the subject's source documents and on the CRF.

6.6 Alcohol Restrictions

Subjects should not consume any alcohol within 24 hours prior to each visit (including screening).

Subjects will be required to limit alcohol consumption throughout the course of the study. Alcohol is limited to no more than 2 drinks per day for the duration of the study. (1 drink being equivalent to 12 ounces (approximately 355 mL) of regular beer, 8 to 9 ounces

(approximately 237 to 266 mL) of malt liquor, 5 ounces (approximately 148 mL) of wine, or 1.5 ounces (approximately 44 mL) of 80 proof distilled spirits).

6.7 Medical Devices

Medical devices for the IV infusion of investigational product (eg, inline filters, IV administration set, infusion pump) will not be provided by Amgen, as routine hemodialysis tubing should be utilized. The Investigator will be responsible for obtaining supplies of these devices.

Medical devices (eg, syringes, sterile needles, alcohol prep pads), that are commercially available are not usually provided or reimbursed by Amgen (except, for example, if required by local regulation). The Investigator will be responsible for obtaining supplies of these devices.

6.8 Product Complaints

A product complaint is any written, electronic or oral communication that alleges deficiencies related to the identity, quality, durability, reliability, safety, effectiveness, or performance of any investigational or non-investigational product(s) or device(s).

Any product complaint(s) associated with an investigational product(s) or non-investigational product(s) or device(s) supplied by Amgen are to be reported according to the instructions provided in the IPIM.

6.9 Excluded Treatments and/or Procedures During Study Period

Treatment with cinacalcet is prohibited during the study through the last study visit (ie, Day 55 (EOS)). Treatment during the study with other medications known to be associated with hypocalcemia is strongly discouraged. Cinacalcet must not have been taken for at least 30 days prior to informed consent.

Subjects should not have a planned kidney transplant during this study.

Subject should not be allowed to donate blood and/or plasma during this study.

6.10 Hemodialysis Treatment Procedures and Concomitant Medications

Subjects should be on maintenance hemodialysis treatment with a prescription for dialysis 3 times per week. Dialysis duration and membrane may be modified in order to maintain adequate hemodialysis treatment (eg, $Kt/V \geq 1.2$ or $URR > 65\%$). If there is a change to the hemodialysis prescription the sponsor should be notified. In the event of a significant permanent change to the hemodialysis prescription, the subject may be

withdrawn from treatment with investigational product as deemed necessary by the sponsor.

Intermittent additional hemodialysis treatment (eg, for ultrafiltration) or changes in hemodialysis schedule (eg, missed/rescheduled treatments or shifts in schedule) are not considered significant changes in hemodialysis treatment prescription.

Subjects must have a prescribed dialysate calcium concentration ≥ 2.25 mEq/L stable for at least 4 weeks prior to screening laboratories, and the dialysate calcium concentration must be maintained ≥ 2.25 mEq/L throughout the study.

Medications used to treat hemodialysis-related symptoms or comorbid conditions should be reported as concomitant medications whenever administered to the subject.

Medications administered at each dialysis session (eg, heparin, diphenhydramine) should be reported on the CRF with a frequency of every hemodialysis (qhd) unless a change in dose or frequency occurs. The following medications used in the delivery of hemodialysis should not be reported on the CRF as concomitant medication:

- local anesthetic for cannulation
- saline prime for the dialysis circuit
- saline or hypertonic saline for management of intradialytic hypotension
- oxygen

7. STUDY PROCEDURES

7.1 Schedule of Assessments

Table 1. Schedule of Assessments

Table 1a. Schedule of Non-laboratory Assessments

Assessment	Screening	Study Visit (Day)																		
		-2	1 (HD)	2	3 (HD)	6 (HD)	8 (HD)	10 (HD)	13 (HD)	15 (HD)	17 (HD)	20 (HD)	22 (HD)	24 (HD)	27 (HD)	28	29/ET ^{a,h} (HD)	34 (HD)	41 (HD)	55 (HD)
Informed consent	X																			
Eligibility	X																			
Medical and surgical history	X																			
Demographics ⁱ	X																			
Prior medications	X	X																		
Body Height ^b	X																			
Body Weight ^b	X	X	X														X			X
Physical exam ^b	X		X							X							X			X
Hemodialysis symptoms ^c	X																			
Investigational product administration ^d			X		X	X	X	X	X	X	X	X	X	X	X					
Vital Signs (BP, HR, RR, TEMP) ^e	X	X	X	X	X	X	X	X	X	X	X	X	X	X	X	X	X	X	X	X
12-lead electrocardiogram ^f	X	X														X				X
Adverse Event Monitoring ^g	X	X	X	X	X	X	X	X	X	X	X	X	X	X	X	X	X	X	X	X
Concomitant Medications	X	X	X	X	X	X	X	X	X	X	X	X	X	X	X	X	X	X	X	X

Footnotes displayed on the next page

ET = early termination; HD = hemodialysis.

- ^a If a treated subject withdraws before completion of dosing, the investigator will make every effort to perform Day 29 assessments as close to 2 days after the last dose of investigational product as possible.
- ^b A physical examination will be performed at screening. Abbreviated physical examinations will be performed on day 1 (unless day 1 occurred more than 2 weeks after screening physical examination), Days 15, 29 and 55. Height will be captured once at screening. Weight will be recorded before dialysis.
- ^c Common symptoms associated with hemodialysis will be captured at screening. Any worsening of hemodialysis symptoms will be reported as an adverse event.
- ^d Investigational product will be administered by intravenous (IV) injection over approximately 30 seconds into the venous line with dialysis rinse back at the end of the dialysis session.
- ^e Subjects will remain seated for at least 10 minutes prior to measurement of predialysis heart rate and blood pressure. Vital signs will include blood pressure, heart rate, respiratory rate, and oral or ear temperature. Vital signs will be obtained pre-dialysis treatments on scheduled dialysis days, and at ET and on Day 55 (EOS).
- ^f Subjects will remain supine for at least 5 minutes prior to recording 12-lead electrocardiogram (ECG). Screening 12-lead ECG will be recorded prior to hemodialysis. The Day -2 12-lead ECG will be recorded within 4 hours after hemodialysis rinse back. After the last dose of investigational product on Day 27, 12-lead ECGs will be recorded between 18 and 30 hours (recorded on day 28) post-dose.
- ^g Adverse events will be monitored and recorded from the dose of investigational product (AMG 416) or placebo. Serious adverse events will be monitored and recorded from the time of informed consent through Day 55.
- ^h After Day 28, hemodialysis will continue on study days 29, 31, 34, 36, 38, 41, 43, 45, 48, 50, 52 and 55; data collection and study procedures will only occur on hemodialysis days 29, 34, 41, and 55(EOS).
- ⁱ Demographic information collected at screening includes sex, age, race, and ethnicity.

Table 1b. Schedule of Laboratory Assessments

Time	Assessment	Study Visit (Day)																			
		Screening	-2	1 (HD)	2	3 (HD)	6 (HD)	8 (HD)	10 (HD)	13 (HD)	15 (HD)	17 (HD)	20 (HD)	22 (HD)	24 (HD)	27 (HD)	28	29/ ET ^a (HD)	34 (HD)	41 (HD)	55 (HD)
Laboratory Assessments																					
Pre HD	Hematology, PT, aPTT ^c	X		X							X							X			X
	Clinical Chemistry	X		X							X							X			X
	Albumin ^d	X	X ^b	X		X		X			X		X		X			X	X	X	X
	Phosphorus	X	X ^b			X		X			X		X		X				X	X	X
	Calcium (cCa) ^d	X	X ^b	X				X			X		X		X			X	X	X	X
	Serum or Urine Pregnancy (females only)	X	X ^b																X		
	Serum FSH ^g (female only)	X																			
	Breath Alcohol Screen	X	X																		
	HIV, Hep C Ab, HBsAg	X																			
	iPTH	X	X ^b	X				X			X		X		X				X	X	X
	25(OH) vitamin D	X																			
	Kt/V or URR ^e	X																			
	Anti-drug antibodies ^f			X														X			X

Footnotes displayed on the next page

HD = hemodialysis; ET = early termination; cCa = albumin-corrected calcium; SDA = Study drug administration ; Kt/V = measure of dialysis adequacy;

URR = urea reduction ratio

- ^a If a treated subject withdraws from study before completion of dosing, the investigator will make every effort to obtain day 29 samples as close to 2 days after the last dose of investigational product as possible.
- ^b If screening albumin, phosphorus, cCa, pregnancy, and iPTH tests occur within 7 days prior to start of IP, then Day -2 lab tests can be waived
- ^c Blood sample for PT and aPTT will be drawn prior to heparin administration for dialysis. Day 1 hematology and coagulation tests will be performed only if day 1 occurs more than 2 weeks after the screening hematology and coagulation tests.
- ^d Serum samples for albumin and calcium for screening and routine monitoring of predialysis cCa. When albumin is less than 4.0 g/dL, the calcium level will be corrected according to the formula: $cCa \text{ (mg/dL)} = \text{total Ca (mg/dL)} + (4 - \text{albumin (g/dL)}) \times 0.8$. Corrected calcium results will inform dosing/dose withholding at the next hemodialysis treatment.
- ^e Perform Kt/V or URR assessment at screening unless a qualifying Kt/V or URR measurement from within 4 weeks prior to screening assessments is available.
- ^f Serum samples for anti-drug antibodies will be collected predialysis on days 1, 29, and 55. Any subjects with positive titers for antibodies to AMG 416 may be asked to return to the clinical research unit to provide additional serum samples.
- ^g Luteinizing hormone and estradiol levels may additionally be collected if deemed necessary for confirmation of postmenopausal status as described in exclusion criteria [section 4.2.4](#)

Table 1c. Schedule of Pharmacokinetic Assessments

Time	Assessment	Study Visit (Day)																			
		Screening	-2	1 (HD)	2	3 (HD)	6 (HD)	8 (HD)	10 (HD)	13 (HD)	15 (HD)	17 (HD)	20 (HD)	22 (HD)	24 (HD)	27 (HD)	28	29/ ET ^a (HD)	34 (HD)	41 (HD)	55 (HD)
Central Laboratory																					
Pre HD	PK			X		X		X			X			X		X		X	X	X	X
SDA + 10 min	PK			X				X			X			X		X					
SDA + 30 min	PK			X												X					
SDA + 60 min	PK			X												X					
SDA + 90 min	PK			X												X					
SDA + 18 to 30 hr	PK				X												X				

HD = hemodialysis; ET = early termination; SDA = Study drug administration.

7.2 General Study Procedures

Study tests and procedures will be performed only after written informed consent is obtained. All screening procedures must be completed within 22 days before investigational product administration (Day 1). Eligible subjects will be admitted to the clinical research facility on Day -2 at which time continued eligibility will be reconfirmed and baseline safety assessments will be performed. Subjects will be administered AMG 416 or placebo on Day 1 after completion of baseline assessments.

In the event that multiple post dose procedures are required to be conducted at the same nominal time point, the following order of precedence will be used to ensure certain post dose safety assessments will not be disturbed by blood draws:

(1) electrocardiogram (ECG) recording; (2) vital signs assessment; (3) PK blood sampling; (4) clinical laboratory tests; and (5) physical examination and physical measurements. Electrocardiograms and vital signs may be conducted up to 15 and 10 minutes, respectively, prior to the nominal time so that PK samples will be collected as close to the nominal time point as possible. The remaining postdose procedures/assessments may be conducted up to 30 minutes after the nominal time.

Every effort should be made to conduct study procedures as scheduled. Acceptable windows for the timing of PK are as follows:

- Plus or minus 2 mins for the 10 min sample
- Plus or minus 5 mins for the 30 min sample
- Plus or minus 10 mins for the 60 min sample
- Plus or minus 15 mins for the 90 min sample
- Plus or minus 4 hours for the 18-30 hour post dose samples

7.2.1 Screening

Screening assessments will be completed after the informed consent form is signed, but prior to initiating treatment with investigational product, in a 22 day screening period.

Screening assessments must be performed within these 22 days prior to the first dose of investigational product. All inclusion and exclusion central laboratory requirements must be met during the 3 weeks prior to randomization. Screening assessments may be repeated up to 2 times during the 3-week screening period, utilizing the same informed consent signature. A new informed consent form must be signed if it has been more than 22 days since the previous signature. Subjects may re-sign a new informed consent form two additional times.

After informed consent is obtained the following procedures will be completed during the screening period according to the Schedule of Assessments:

- Non Laboratory Assessments:
 - Confirmation of informed consent
 - Eligibility
 - Demographics (sex, age, race, ethnicity)
 - Medical and surgical history
 - Prior (from 4 weeks prior to informed consent) and concomitant medication
 - Body weight (before dialysis if on a dialysis day)
 - Height
 - Physical examination
 - Hemodialysis symptoms
 - Vital signs (BP,HR,RR, TEMP)
 - 12 lead ECG recording
 - Serious adverse event monitoring
 - B ultrasound to exclude ovarian cancer (Optional at PI's discretion)
- Laboratory assessments (all pre-hemodialysis samples)
 - Clinical hematology
 - Clinical chemistry
 - PT, aPTT
 - Albumin, Phosphorus, Calcium (cCa)
 - Serum or urine pregnancy test (women of child-bearing potential only; within 7 days prior to first study drug administration)
 - Serum FSH (females only)
 - Breath alcohol screen
 - HIV, Hepatitis C Antibody, Hepatitis B surface antigen
 - iPTH
 - 25(OH) vitamin D
 - Kt/V or URR

Subjects who meet the eligibility criteria after completion of all screening, Day -2 procedures will be considered enrolled in the study.

If screening albumin, phosphorus, cCa, pregnancy, and iPTH tests occur within 7 days prior to start of IP, then Day -2 lab tests can be waived.

Day -2 assessments will be performed 2 days before investigational product administration. Day -2 assessments will include recording the date and time of the last hemodialysis treatment before investigational product administration.

Evaluations obtained as part of routine medical care may be performed prior to informed consent and may be used in place of the study specific evaluations, provided they are performed within 22 days prior to Day 1 and meet the time windows described above.

7.2.2 Day -2

Two days before dosing (day -2) the following baseline procedures will be performed and confirmed to meet eligibility requirement :

- Non Laboratory Assessments:
 - Medication use over 4 weeks prior to informed consent
 - Vital signs (BP, HR, RR, TEMP)
 - Body weight
 - 12 lead electrocardiogram
 - Serious adverse event monitoring
 - Concomitant medications
- Laboratory assessments:
 - Albumin, Phosphorus, Calcium (cCa)
 - Serum or urine pregnancy test (women of child-bearing potential only)
 - Breath alcohol screen
 - iPTH

Eligible subjects will be randomized prior to dosing to receive either AMG 416 or placebo in a 3:1 ratio.

7.2.3 Treatment (Day 1-27) and Follow up Periods (Day 28-55)

On day 1 the following predose activities will be conducted:

- Non Laboratory Assessments:
 - Body weight (before dialysis)
 - Physical examination
 - Vital signs (BP,HR,RR, TEMP)
 - Adverse event monitoring
 - Concomitant medications
- Laboratory assessments and predose collections (pre-hemodialysis samples):
 - Hematology, PT, aPTT
 - Clinical chemistry

- Calcium (cCa)
 - iPTH
 - Albumin
 - Anti-Drug Antibodies
 - Pre-hemodialysis PK sample
- IP Administration, Dialysis and Pharmacokinetic Schedule

IP will be administered at the end of dialysis on Study Days 1, 3, 6, 8, 10, 13, 15, 17, 20, 22, 24, 27 (12 doses). Investigational product will be administered by bolus injection into the venous line of the dialysis circuit at the end of hemodialysis treatment, prior to or during rinse-back with each hemodialysis session (ie, 3 times per week). At least 150 mL of rinse back volume should be administered after investigational product injection to ensure investigational product reaches the systemic circulation. If rinse-back is completed and investigational product was not administered, then investigational product may be administered intravenously followed by at least 10 mL saline flush volume. The end of hemodialysis treatment is defined as when the prescribed hemodialysis treatment time is completed (ie, remaining time on dialysis (RTD) is zero) or when the arterial flow is stopped (eg, arterial line is clamped or disconnected to discontinue treatment), whichever occurs first. If a regularly scheduled hemodialysis session is missed and subsequently rescheduled, investigational product will not be administered at the rescheduled hemodialysis session. For example, a subject on a Mon/Wed/Fri schedule who misses a Wed session will be dosed on Mon and Fri; if a make-up session is added on Thu and the subject maintains the regularly scheduled session on Fri, the subject will only be dosed on Mon and Fri and not on Thu. If an additional hemodialysis treatment is needed intermittently (eg, fourth treatment during a week for ultrafiltration) then an additional dose of investigational product will not be administered during the extra dialysis session. Additional details will be provided in IPIM. Investigational product must only be administered intravenously; it must not be administered via any other route. Investigational product must not be administered concurrently with any other intravenous medications. If there is a significant permanent change to the hemodialysis prescription, then the sponsor will be notified and subject may be withdrawn from treatment with investigational product.

Blood samples for the determination of PK parameters will be collected on Day 1 and 27 at predialysis, and at 10, 30, 60 and 90 min postdose and on Day 2 and 28 between

18 and 30 h after study drug administration, and at predialysis on Days 3, 8, 15, 22, 29, 34, 41, and 55 and at 10 min postdose on Days 8, 15 and 22.

The date and time of hemodialysis treatment will be recorded throughout the treatment period. When a visit corresponds to a dialysis day, study procedures should be completed prior to hemodialysis.

Following completion of all study procedures on Day 1, subjects will be discharged with instructions to return to the research facility at specified time points for dosing, collection of blood samples for PK, PD and completion of safety assessments (including blood samples for antibody analysis) through the end of the study according to the schedule of assessments.

- Other Predialysis Assessments after Day 1:
 - Body Weight (before dialysis) on Days 29 and 55
 - Physical exam on Days 15, 29 and 55
 - Vital signs (BP,HR,RR, TEMP) – all visits
 - 12 lead Electrocardiograms (ECG) on Day 28 and Day 55 (EOS)
 - Adverse event monitoring (including serious adverse events and deaths) – all visits
 - Concomitant medications – all visits
 - Pregnancy test on Day 34
 - Hematology, PT, aPTT on Days 15, 29 and 55
 - Clinical Chemistry on Days 15, 29 and 55
 - Albumin on Days 3, 8,15, 22, 27, 29, 34, 41, 55
 - Phosphorus on Days 3, 8, 15, 22, 27, 34, 41, 55
 - Calcium (cCa) on Days 8, 15, 22, 27, 29, 34, 41, 55
 - iPTH on Days 8, 15, 22, 27, 34, 41, and 55
 - Anti-Drug Antibodies on Day 29 and 55

Subjects will be followed for safety throughout the 4-week treatment period and for 4 weeks after the last dose of investigational product to Day 55 (EOS). Dosing with investigational product may be suspended, for low predialysis iPTH or cCa, symptomatic hypocalcemia, or other drug-related adverse events.

Subjects who test positive for antibodies to AMG 416 at the EOS visit will be asked to return for additional follow-up testing (see [section 7.4](#))

If there is a clinically significant clinical or laboratory abnormality that requires monitoring, subjects will be followed until resolution of the abnormality or until it is considered stable.

Subject participation is complete once Day 55 end-of-study (EOS) procedures are performed.

For a full list of study procedures, including the timing of each procedure, please refer to the [Schedule of Assessments](#).

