2.3 Risk Assessment

Safety reporting for all subjects in open-label and blinded studies completed as of 10 November 2017 and the investigators brochure have identified the following risks:
Important identified risks:

- Hypocalcemia
- Worsening heart failure
- QT prolongation secondary to hypocalcemia

Important potential risks:

- Ventricular arrhythmias
- Infusion and hypersensitivity reactions
- Convulsions (seizures)
- Adynamic bone
- Co-administration of cinacalcet (HCl) and etelcalcetide

The important identified risk is hypocalcemia, which will be mitigated in the protocol by close monitoring, and treatment as required. Coadministration of cinacalcet and AMG 416 is contraindicated until further studies inform the safety of simultaneous administration of these agents. The likelihood of these risks occurring with the planned dose for this study is expected to be low. In this study, cinacalcet will be prohibited from 30 days prior to informed consent and throughout the study.

Please refer to the [Investigator's Brochure](#), Section 7 for additional information for the investigator.

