9.3 Changes in Serum Calcium and Symptomatic Hypocalcemia

Investigators should assess subjects for the onset of signs and symptoms associated with low serum calcium (see [Section 6.3.1.1](#)) at each visit. When observed,

“hypocalcemia” should be reported as the adverse event, and the associated signs and symptoms will also be captured.

Any serum calcium (corrected) (cCa) ≥ 7.5 and < 8.3 mg/dL can be reported as low blood calcium; however, low a calcium result does not need to be reported as an adverse event if no action is taken, and the value is not deemed clinically significant by the investigator. If the cCa is < 8.3 mg/dL and there are symptoms of hypocalcemia then the event is to be reported as hypocalcemia and considered a serious adverse event. The associated signs and symptoms should also be captured.

Also, any cCa level < 7.5 mg/dL is to be reported as a serious adverse event of low blood calcium if there are no associated signs and symptoms, but it is to be reported as hypocalcemia if there are associated symptoms. The associated signs and symptoms should also be captured.

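### Adding total calcium to the Day 3 blood draw would give a first on-treatment corrected calcium after one dose instead of three, at low cost; the present schedule is not an error

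*Protocol*

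**What the plan says.** Section 7.2.3 of the protocol lists the predialysis laboratory days after Day 1:

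- calcium: "Calcium (cCa) on Days 8, 15, 22, 27, 29, 34, 41, 55"
- albumin: "Albumin on Days 3, 8,15, 22, 27, 29, 34, 41, 55"
- intact PTH: "iPTH on Days 8, 15, 22, 27, 34, 41, and 55"

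Phosphorus is also listed on Day 3. Table 1b agrees for the first week: the albumin and phosphorus rows are marked on Day 3 and the calcium row is not. The chemistry panel, which contains calcium (Table 2), is drawn at screening and on Days 1, 15, 29 and 55, so it supplies no Day 3 value.

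Footnote d of Table 1b gives the purpose of the paired samples: "Serum samples for albumin and calcium for screening and routine monitoring of predialysis cCa". It also says how results are used: "Corrected calcium results will inform dosing/dose withholding at the next hemodialysis treatment". Section 7.2.3 adds: "Dosing with investigational product may be suspended, for low predialysis iPTH or cCa". Section 2.3 states: "The important identified risk is hypocalcemia", to be mitigated by close monitoring. Under Section 9.3, "any cCa level < 7.5 mg/dL is to be reported as a serious adverse event of low blood calcium" when there are no signs or symptoms.

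**The concern.** Albumin is needed to correct calcium, and footnote d describes the two samples together. On Day 3 only albumin is drawn, so cCa cannot be obtained for anyone. Subjects with albumin below 4.0 g/dL have no calcium to correct, and the others have no total calcium to read directly. The rationale for Amendment 2 shows that the sponsor has thought of the tests as a pair, since it added albumin on Days 1 and 29 because corrected calcium was needed.

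At stake is the earliest laboratory check on the drug's expected effect. cCa is a named secondary safety measure and a stated ground for suspending doses. A fall below 7.5 mg/dL without symptoms is reportable as serious, yet symptom checks at visits would not find it. Tests done only when clinically indicated would not reliably find it either. In the placebo-controlled phase 3 trials (Section 2.2.2), decreased blood calcium was reported in 63.8% on drug and 10.1% on placebo. Those trials ran 26 weeks, so the figures show that the event is common but say nothing about the first week at a fixed 5 mg.

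**Working it through.** **Inputs**

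- Dosing days (Section 7.2.3): 1, 3, 6, 8, 10, 13, 15, 17, 20, 22, 24, 27. The count is 12, as the protocol states.
- Post-Day 1 calcium days (Section 7.2.3): 8, 15, 22, 27, 29, 34, 41, 55.
- Post-Day 1 albumin days (Section 7.2.3): 3, 8, 15, 22, 27, 29, 34, 41, 55.
- Samples are taken before dialysis and the dose is given at its end, so a sample precedes the same day's dose.
- A cCa result informs the next dialysis session (footnote d).

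In the text available here, the Table 1b marks for late treatment seem to fall on Days 20 and 24, where Section 7.2.3 has Days 22 and 27. This may be a reading fault in the table. The Section 7.2.3 days are used below, and the point does not affect Days 3 to 8.

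**Step 1: which visit lacks calcium.** Albumin days minus calcium days leaves Day 3 alone.

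**Step 2: doses before the first on-treatment cCa.** For a predialysis sample on day s, this is the number of dosing days earlier than s.

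- Now, s = 8: Days 1, 3, 6, so 3 doses. Elapsed time 8 − 1 = 7 days.
- With Day 3 calcium, s = 3: Day 1, so 1 dose. Elapsed time 3 − 1 = 2 days.

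**Step 3: first dose the result can inform.**

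- Now: Day 10. Doses already given: Days 1, 3, 6, 8, so 4. The first informed dose is dose 5.
- With Day 3 calcium, reported by Day 6: doses already given are Days 1 and 3, so 2. The first informed dose is dose 3.
- With Day 3 calcium, reported only after the Day 6 session: doses already given are Days 1, 3, 6, so 3. The first informed dose is dose 4, on Day 8.

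**Step 4: doses resting on each cCa result.** The Day 1 dose rests on the screening or Day -2 value.

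| Result | Now | Day 3 added, reported by Day 6 | Day 3 added, reported by Day 8 |
|---|---|---|---|
| Screening or Day -2 | 1 | 1 | 1 |
| Day 1 | 3 (Days 3, 6, 8) | 1 (Day 3) | 2 (Days 3, 6) |
| Day 3 | – | 2 (Days 6, 8) | 1 (Day 8) |
| Day 8 | 3 (Days 10, 13, 15) | 3 | 3 |
| Day 15 | 3 (Days 17, 20, 22) | 3 | 3 |
| Day 22 | 2 (Days 24, 27) | 2 | 2 |
| Total | 12 | 12 | 12 |

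**Step 5: time to report.** Day 3 to Day 6 is 3 calendar days, and Day 8 to Day 10 is 2. But Day 3 to Day 6 is the long gap of the week. On the Mon/Wed/Fri example in Section 7.2.3 it runs from Friday to Monday, with no weekday between, while Day 8 to Day 10 runs from Wednesday to Friday. The documents state no laboratory turnaround, so it cannot be said whether the Day 6 target is easier or harder to meet than the present Day 10 target.

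**Step 6: assays.** About 32 subjects × 1 = about 32.

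**The case against.** The strongest case against acting is that the schedule is coherent as it stands. cCa is drawn weekly on Days 1, 8, 15 and 22, and the first week has the same density as the next two, 3 doses per result. Intact PTH is not drawn on Day 3 either. The 5 mg dose is the phase 3 starting dose, adjusted there only every 4 weeks, and Section 2.4 describes it as well tolerated in phase 2. Day 3 follows the least cumulative dosing of any on-treatment dialysis visit: after twelve 5 mg doses, exposure is about 2-fold (Cmax) to 3-fold (AUClast) that of Day 1 (Section 2.2.2.1). No cCa threshold for withholding is given, so a Day 3 value would feed discretionary judgement.

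Other safeguards also apply. Signs and symptoms of low calcium are assessed at each visit (Section 9.3). Subjects with cCa below 8.3 mg/dL are excluded (Section 4.2.1), and dialysate calcium stays at or above 2.25 mEq/L (Section 6.10). Calcium supplements and active vitamin D are standard of care in both arms (Section 3.1). Unscheduled tests are allowed (Sections 7.3.10 and 7.3.19).

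All of this stands, and it limits the weight of the point. It does not remove it, because none of these measures reliably detects an asymptomatic fall in the first week, and the serum is already drawn.

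A reader might go further and infer that calcium was left off Day 3 by mistake. The documents do not show that. Albumin is summarized as a variable in its own right (SAP 9.6.2), the drug binds covalently to albumin (Section 2.2.1.2), and the exploratory text is not visible, so the full purpose of the Day 3 albumin is unknown.

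**Conclusion.** This is a minor, cheap improvement. The schedule counts are certain: the first scheduled on-treatment cCa would move from 7 days and 3 doses after the start to 2 days and 1 dose. The first dose it can inform would move from dose 5 to dose 3, or to dose 4 if the result is not reported over the long gap. The Day 6 timing rests on a laboratory turnaround that the documents do not give.

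The benefit is not quantified. The documents give no first-week rate of low cCa at a fixed 5 mg, so the number of events detected or doses changed cannot be estimated and may be small. A reader might also infer that subjects are unmonitored or unsafe before Day 8. That does not follow, given the visit-by-visit symptom checks, the entry limit and the provision for unscheduled tests. The claim is only that a useful check on the main identified risk is available at low cost and is not taken.

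**What to change.** Add total calcium (cCa) on Day 3 in Table 1b and in the Section 7.2.3 list, run on the serum already drawn for albumin and phosphorus. Review the result at the Day 6 session under the existing footnote d, or at Day 8 if it is not yet back. Confirm with the laboratory whether results from the Day 3 sample can be reported before Day 6. No new dosing rule is proposed.

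The cost is about 32 extra assays, with no new visit or needle stick. The two-place amendment needs investigator agreement and IRB approval (Section 12.1), and could be bundled with another amendment. The SAP needs no change, because Section 9.6.2 already summarizes cCa at every scheduled visit.
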